9. DATA SAFETY MONITORING BOARD

Not applicable.

10. STATISTICAL ANALYSIS

The primary analysis consists of a comparison of outcomes between de PENELOPE CTRL and the original PENELOPE intention to treat population. Baseline characteristics of the cohorts will be presented. To assess for potential remaining imbalances between the cohorts a t-test and Chi-squared test will be used for continuous and dichotomous variables, respectively.

In case of imbalance in patient characteristics between the cohorts, a step-wise approach will be used to correct for this.

- First, a propensity score is derived to asses for membership of trial. Second, a propensity score is derived on the baseline criteria.
- If the distribution of the propensity scores is dissimilar between PENELOPE CTRL and PENELOPE adjustment for differences in propensity function is done in two methods.
 - First, logistic regression analysis with propensity score as co-variate.
 - Second, stratified analysis with deciles of the propensity score.

Percentages are converted to Odds Ratio to allow for multivariable analysis. Missing values are reported and appropriately imputed in the statistical models.

Statistical analysis will be formalised in the SAP, as well as the statistical methods to be used for endpoint analysis. For comparison between the PENELOPE and PENELOPE CTRL cohort, the same additional exclusion criteria were applied: 'known intolerance for alirocumab' and 'active PCSK9-I therapy at baseline'. Life expectancy <1 year was omitted as this could not be determined reliably from the medical records retrospectively. For the primary outcome and secondary outcomes b, c and e (investigating the effects of oral LLT), patients will be excluded as soon as they start using PCSK9i.

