 - if LDL-C 2.6-3.6 mmol/L, alirocumab 75 mg or 150 mg Q2W had to be initiated (dosing at the investigator's discretion)
 - if LDL-C >3.6 mmol/L, alirocumab 150 mg Q2W had to be initiated.

PENELOPE was designed to demonstrate feasibility and efficacy of guideline-based protocolized LLT in the Netherlands.

PENELOPE-CTRL is designed to document real life LLT and resulting LDL-C target attainment in the Netherlands.

Comparison of PENELOPE and PENELOPE-CTRL will demonstrate whether the strategy of protocolized guideline based LLT results in a higher incidence of target LDL-C levels in secondary prevention at set time points, and quantify this difference.

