6. STUDY POPULATION

a. POPULATION

All patients fulfilling the in- and exclusion criteria in the participating centres will be included in the PENELOPE-CTRL cohort (Registry). Participating sites are part of the WCN research network and have not participated in PENELOPE. These are all non-academic cardiovascular research centres, providing regional cardiovascular hospital care with a regional CVRM function. All sites are using the same standard operating procedures for clinical research.

Inclusion criteria are identical to the Penelope trial, with the exception of the introduction of a maximum age of 70 years in PENELOPE-CTRL. (Table 1) In PENELOPE, patients >70 years of age were required to have a clinical frailty score (CFS) ≤ 3 . As retrospective electronic medical records data do not allow for accurate determination of the CFS, all patients >70 years will be excluded in PENELOPE-CTRL. For the comparative analysis the CTRL population will be compared to the Penelope patients ≤ 70 years old (N=663). Furthermore, only patients who were alive at discharge will be registered.

b. INCLUSION CRITERIA

- Age >18 and ≤ 70 years
- Alive at hospital discharge after admission for (N)STEMI between 1-1-2019 and 31-08-2020

- Planned for follow-up at a participating PENELOPE CTRL site
- History of T2DM and/or history of ASCVD defined as either one of:
 - cerebrovascular disease/ event: transient ischemic attack, cerebral infarction, amaurosis fugax, retinal infarction
 - Coronary artery disease/ event: unstable angina pectoris, MI, ACS, coronary revascularization (coronary angioplasty or surgical procedure for coronary bypass)
 - Peripheral artery disease (symptomatic and documented obstruction of a distal extremity artery or surgical intervention (percutaneous transluminal angioplasty, bypass or amputation)

Table 1. Inclusion criteria PENELOPE and PENELOPE CTRL, and PENELOPE analysis population

	PENELOPE	PENELOPE (cohort compared to CTRL)	PENELOPE CTRL
Age	≥18 years, ≤70 years	≥18 years, ≤70 years	≥18 years, ≤70 years
	>70 years and CFR≤3	-	-
history of ASCVD	✓	✓	✓
T2DM	✓	✓	✓
admission for (N)STEMI	✓	✓	✓

c. EXCLUSION CRITERIA

- Pregnant and lactating women

Participation in lipid modifying drug trials up to two years after index CVE.

d. PATIENT SELECTION

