12. ETHICAL CONSIDERATIONS

a. Regulation statement

In the Netherlands, there is no regulation for non-interventional studies like the Medical Research Involving Human Subjects Act (WMO) for interventional studies. In the absence of a regulation, a

framework of standards (Normenkader) has been put in place to ensure non-interventional studies are properly conducted. These standards aim to provide a framework for those who initiate the study, for those who assess the legitimacy of the study and those who conduct the study. PENELOPE-CRTL will be conducted in accordance with these standards. PENELOPE- CTRL will be used as a control cohort for PENELOPE. PENELOPE is evaluated as a “WMO-obligated” protocol, requiring informed consent. PENELOPE-CTRL is submitted in the DCRF route as a pharma funded investigator initiated nWMO cohort, and evaluated by the MEC-U who also was the central ethic committee for PENELOPE.

b. Recruitment and consent

Retrospective data will be used in this analysis and therefore recruitment and consent are not applicable. Informed Consent has been waived by the MEC_U under the condition that all participating centres have a local opt-out for use of data on the website. This will be documented in the Green Light process before start of data collection.

c. Benefits and risks assessment, group relatedness

Not applicable.

d. Compensation for injury

Not applicable.

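### Confounding adjustment depends on baseline tests and then on a propensity-score check, so the primary comparison of two non-randomised cohorts can be left unadjusted

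*Protocol*

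**What the plan says.** Protocol section 10 names the primary analysis without any adjustment: "The primary analysis consists of a comparison of outcomes between de PENELOPE CTRL and the original PENELOPE intention to treat population". To look for imbalance, "a t-test and Chi-squared test will be used for continuous and dichotomous variables, respectively". The next paragraph begins "In case of imbalance in patient characteristics between the cohorts, a step-wise approach will be used to correct for this". Within that approach a propensity score is derived, and then comes a second condition: "If the distribution of the propensity scores is dissimilar between PENELOPE CTRL and PENELOPE adjustment for differences in propensity function is done". Two methods follow: logistic regression with the score as covariate, and stratification by its deciles. Neither is named as the primary one.

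No significance level is given for the baseline tests, and no criterion defines imbalance or dissimilar.

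The protocol also states how the cohorts come to differ:
- Section 6, on hospitals: "Participating sites are part of the WCN research network and have not participated in PENELOPE".
- Section 12, on consent: PENELOPE required informed consent, whereas for the control cohort "Informed Consent has been waived by the MEC_U under the condition that all participating centres have a local opt-out".
- Section 10, on eligibility: "Life expectancy <1 year was omitted as this could not be determined reliably from the medical records retrospectively".

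Section 3 sets the ambition: "Comparison of PENELOPE and PENELOPE-CTRL will demonstrate whether the strategy of protocolized guideline based LLT results in a higher incidence of target LDL-C levels", and adds that the difference will be quantified.

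**The concern.** Confounding has to be assumed here, because cohort membership follows the hospital's participation, the patient's consent in one cohort only, and eligibility rules that are not quite the same. A baseline test answers a different question from the one that matters. Its p-value depends on sample size and takes no account of how strongly a variable predicts LDL-C target attainment, so a non-significant result does not show that confounding is absent.

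Under the written rule, the form of the headline estimate is decided by the data. The unadjusted estimate is kept in exactly those samples where several modest differences in the same direction each escape detection. The second condition can also block adjustment after imbalance has been found, on a judgement for which the protocol gives no rule.

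**Working it through.** **The rule as written**

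1. Tests show no imbalance: the step-wise approach does not start, and the comparison is unadjusted.
2. Imbalance is found but the propensity-score distributions are not judged dissimilar: the comparison is unadjusted.
3. Both conditions are met: two adjusted analyses, with no primary one named.

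No other section commits to an adjusted primary comparison. The protocol gives no power figure, alpha or effect size, so there is no stated number to reproduce. What follows is illustration.

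**How often the first condition is met**

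Inputs: 663 PENELOPE patients aged 70 or younger (section 6a); 700 to 1200 control candidates (section 6d), with 950 as midpoint; two-sided test level 0.05 (assumption).

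For a true standardised difference d, SE = sqrt(1/663 + 1/n2), and the chance of a significant test is P(|Z + d/SE| > 1.96).

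| n2 | SE | flagged, d = 0.10 | flagged, d = 0.20 |
|---|---|---|---|
| 700 | 0.0542 | 45.4% | 95.8% |
| 950 | 0.0506 | 50.6% | 97.7% |
| 1200 | 0.0484 | 54.2% | 98.5% |

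An observed standardised difference up to 1.96 × 0.0542 = 0.106 (n2 = 700) or 1.96 × 0.0484 = 0.095 (n2 = 1200) would count as no imbalance. For a binary characteristic at 50% versus 55%, the corresponding test flags the difference in 46% (n2 = 700) to 54% (n2 = 1200) of samples.

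**What happens when no test is significant**

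Assumptions: eight independent normal covariates, each shifted 0.06 SD in the same direction, each with log odds ratio 0.3 per SD; intercept set to 65% attainment; no cohort effect (true OR 1.00); 4000 runs per n2. Any baseline p < 0.05 leads to logistic regression with the estimated propensity logit as covariate; otherwise the estimate is unadjusted. The second condition is not modelled, because the protocol gives no rule for it.

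| | n2 = 700 | n2 = 950 | n2 = 1200 |
|---|---|---|---|
| Runs with no significant test | 17.8% | 13.0% | 12.1% |
| Unadjusted OR in those runs | 1.093 | 1.083 | 1.095 |
| Rejection at 5%, unadjusted, those runs | 11.4% | 9.8% | 13.8% |
| Propensity-adjusted OR, same runs | 1.000 | 0.994 | 1.006 |
| Rejection, adjusted, same runs | 4.2% | 4.6% | 4.8% |
| Conditional rule, all runs: OR | 1.014 | 1.009 | 1.010 |
| Conditional rule, all runs: rejection | 5.3% | 4.9% | 5.5% |
| Always adjusted, all runs: rejection | 4.0% | 4.2% | 4.4% |

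**Sensitivity of these figures**

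- Random signs (n2 = 950): OR 1.008 in the runs with no significant test, so the average bias disappears.
- Eight covariates at 0.10 SD (n2 = 950): the first condition is missed in only 0.2% of runs.
- Four covariates at 0.08 SD (n2 = 950): missed in 17.0% of runs, OR 1.06 in those, 1.01 overall.
- Log odds ratio halved to 0.15, eight covariates (n2 = 950): OR 1.05 and rejection 7.1% in the missed runs, 5.2% overall.
- Fifteen covariates: missed in 2.0-3.5% of runs, OR 1.15-1.18 in those, 1.00 overall.
- A separate set of runs with three to five covariates at 0.08 SD and an odds ratio of 1.5 per SD (n2 = 700 and 1200): no significant test in 22-33% of runs with three covariates and 8-16% with five. In those runs the unadjusted difference was biased by 1.4-2.6 percentage points, with rejection of about 9-19%.
- A single covariate at 0.10 SD (odds ratio 1.5 to 3 per SD): bias of about 0.5-1.3 points and rejection of 5-7% when its test is not significant.

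**The case against.** **Other wording may imply adjustment.** Section 10 also says, with no condition attached, that percentages are turned into odds ratios so that multivariable analysis is possible, and it mentions imputation in the models. That could be read as planning a multivariable analysis in any case. But it fixes a scale and names neither a model nor covariates, so it does not override the two conditions.

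**The p-value trigger is inferred.** The text does not say outright that a non-significant test means balance. This is correct, though it is the natural reading of consecutive sentences. If it is rejected, the first condition has no criterion at all and adjustment becomes discretionary.

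**The SAP may settle it.** It is not available, and it may define the terms. But the conditional rule stands in the protocol itself, and a SAP with unconditional adjustment would contradict it.

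**The harm is small on average.** This stands. The raised rejection rates apply only within the minority of runs where no test is significant, under assumed confounder strengths. Large imbalances are nearly always caught by the first condition.

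**Similar propensity scores mean little to adjust.** If the distributions really are similar, the covariates in the score are roughly balanced and adjustment changes little. This is fair, but it is no reason to withhold adjustment, and the undefined judgement remains.

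**The expected sources of confounding are not adjustment variables.** Hospital, consent and life expectancy would not be removed directly. This also stands, and it belongs in a limitation statement. Adjustment can still address differences they produce in measured characteristics.

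**Conclusion.** The concern holds. Followed as written, section 10 can leave the primary comparison of two non-randomised cohorts unadjusted, and whether it does so depends on the data and on two undefined terms. The flag rates for a standardised difference (45-54% at 0.10, 96-99% at 0.20) follow from the stated cohort sizes and an assumed 0.05 level. The simulated consequences rest on assumed number, direction and strength of confounders: appreciable in the samples where no test is significant, close to nominal over all samples. The effect of the second condition cannot be sized from the protocol. This is a change that should be made, not a flaw that invalidates the study. The reason is that the choice of headline estimate should be fixed in advance, not that a large average bias has been shown.

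**What to change.** In section 10, and in the SAP to match, make one prespecified adjusted comparison the primary analysis regardless of baseline test results and of how the propensity-score distributions look. It can be a propensity-score model or a direct covariate model, but one method should be named as primary and its covariates listed. Suitable variables are already in the planned data collection (study parameters in section 2; section 7): age, index event, T2DM, prior ASCVD, baseline LDL-C and baseline lipid-lowering therapy.

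Describe balance with standardised differences instead of using tests as a trigger, and keep the unadjusted comparison as descriptive. A standardised risk difference with confidence interval may be reported beside the odds ratio, but this is optional.

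State as limitations that patient-level adjustment does not remove hospital-level confounding, nor unmeasured differences arising from consent and from the omitted life-expectancy criterion.

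The cost is wording and slightly more analysis work. No new data are needed.

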2. ABSTRACT

Rationale: Guideline recommended evidence-based clinical care correlates with improved patient outcomes. In real life care, however, adherence to guideline recommendations remains suboptimal. In real life, patients may receive suboptimal treatment and as a result treatment targets are not always met. To support and improve secondary prevention for cardiovascular disease, PENELOPE and PENELOPE-CTRL are designed to support guideline implementation on lipid management and provide valuable feedback to care-givers on real world data.

The recent PENELOPE study was designed to determine the effect of a protocolized, Dutch-, and European Society of Cardiology (ESC) guidelines based strategy of stepwise intensified lipid management in patients at very high risk for Acute coronary syndrome (ACS). In PENELOPE 22 Dutch non-academic hospitals, members of the WCN investigator network, implemented a protocol guided guideline approach in a consecutive cohort of very high-risk patients admitted for ACS over the period 01-01-2019 to 31-08-2020. Lipid values and medication strategy are collected at baseline (index ACS), and after three months and one year post ACS, in order to establish the percentage of patients on target Low density lipoprotein cholesterol (LDL-C).

The current PENELOPE-CTRL study on the other hand, is designed to serve as a contemporary control cohort for PENELOPE. PENELOPE-CTRL is a retrospective observational study, creating a contemporary snapshot of real-life lipid management for secondary prevention in very high-risk patients. PENELOPE-CTRL will collect data in similar hospitals who did not participate in the PENELOPE trial.

To allow comparison of these two strategies, protocol guided versus real life implementation of the cholesterol treatment guidelines, both cohorts include similar patients, and similar data will be collected (e.g., lipid lowering drugs, lipid panels) . Analysis will be done at similar time points. Comparing the real-life data from PENELOPE-CTRL with the data from the PENELOPE study will quantify the effect of a strategy of protocolized guideline-based lipid management with regards to the incidence of target LDL-C levels in very high-risk patients, 3 months and one year after hospitalisation with a myocardial infarction.

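### Hospitals are nested in cohort, but the between-cohort outcome comparison in Section 10 is described at patient level only; in that form it understates the standard error if hospitals differ in LDL-C target attainment

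*Protocol*

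**What the plan says.** **Where the patients come from.** Protocol Section 2 says of the intervention cohort: "In PENELOPE 22 Dutch non-academic hospitals, members of the WCN investigator network, implemented a protocol guided guideline approach". Section 6a says of the control cohort: "Participating sites are part of the WCN research network and have not participated in PENELOPE". No hospital contributes to both cohorts.

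**How the cohorts are compared.** Section 10 makes the comparison of outcomes between the two cohorts the primary analysis. Adjustment is conditional on two steps. The first is: "In case of imbalance in patient characteristics between the cohorts, a step-wise approach will be used to correct for this". The second begins: "If the distribution of the propensity scores is dissimilar between PENELOPE CTRL and PENELOPE adjustment for differences in propensity function". Two outcome analyses then follow: "First, logistic regression analysis with propensity score as co-variate" and "Second, stratified analysis with deciles of the propensity score". The effect measure is set by "Percentages are converted to Odds Ratio to allow for multivariable analysis".

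**What is left open.** Section 10 names no hospital term, random effect or clustered variance, and no other section does. It also gives no variance estimator, interval or significance level for outcomes. It closes with a deferral: "Statistical analysis will be formalised in the SAP, as well as the statistical methods to be used for endpoint analysis". That SAP is not at hand.

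**The concern.** What is compared is a way of organising lipid management, and it was delivered by hospital. Every patient in a given hospital is in the same cohort. If hospitals differ in how often their patients reach target, for reasons the patient covariates do not capture, those differences go straight into the between-cohort contrast. Adding patients within the same hospitals does not average them out. The information on the contrast is limited by the number of hospitals.

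A patient-level logistic model or a decile-stratified analysis in ordinary form counts every patient as independent. A propensity score built from patient baseline data does not repair this, because the variation at issue lies between hospitals. An unadjusted patient-level comparison, which would carry the result if no imbalance were found, has the same problem.

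At stake is the stated precision of the odds ratio for the primary outcome and the target-attainment secondary outcomes. Section 13j foresees use of the results in discussions with health authorities and insurers, where an interval that is too narrow would matter. The baseline t-tests and chi-squared tests are not part of this point.

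**Working it through.** The protocol has no sample size calculation, ICC or error rate, so there is no figure of its own to reproduce. The check asks how far an independent-patient analysis would be off.

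**Inputs from the protocol**
- PENELOPE comparison cohort: 663 patients (Section 6a).
- PENELOPE hospitals: 22 (Section 2).
- CTRL candidates: 700-1200, before eligibility is confirmed (Section 6d).

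**Assumptions, not in the protocol**
- All 22 hospitals contribute to the 663.
- There are 8 to 30 CTRL hospitals.
- The residual ICC is on the proportion scale and equal in both cohorts.
- Hospitals within a cohort are of equal size.
- The test is two-sided at 5%.

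**Formulas**
- Mean hospital size: m1 = 663/22 = 30.1; m2 = N2 / number of CTRL hospitals.
- Design effect per cohort: D = 1 + (m − 1) × ICC.
- True SE / model SE: r = sqrt[(D1/663 + D2/N2) / (1/663 + 1/N2)].
- Actual error: 2 × [1 − Φ(1.96/r)].

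**Worked case: 15 CTRL hospitals, 950 CTRL patients, ICC 0.01**
- D1 = 1 + 29.14 × 0.01 = 1.291.
- m2 = 950/15 = 63.3, so D2 = 1 + 62.33 × 0.01 = 1.623.
- Numerator: 1.291/663 + 1.623/950 = 0.001948 + 0.001709 = 0.003657.
- Denominator: 1/663 + 1/950 = 0.002561.
- r = sqrt(0.003657/0.002561) = sqrt(1.428) = 1.19.
- Actual error = 2 × [1 − Φ(1.64)] = 10.1%.
- Effective sample sizes: 663/1.291 = 513 and 950/1.623 = 585.

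**Range.** The low end is 30 CTRL hospitals with 700 patients; the high end is 8 with 1200.

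| ICC | True SE / model SE | Actual error of a nominal 5% test |
|---|---|---|
| 0.001 | 1.01-1.04 | 5.3-5.8% |
| 0.005 | 1.06-1.17 | 6.5-9.3% |
| 0.01 | 1.12-1.31 | 8.1-13.5% |
| 0.02 | 1.23-1.56 | 11.1-20.9% |
| 0.05 | 1.51-2.14 | 19.5-36.0% |

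Unequal hospital sizes (assumed coefficient of variation 0.5) raise these to 5.4-6.0%, 8.9-15.5% and 22.7-40.3% at ICC 0.001, 0.01 and 0.05. If only 500 CTRL patients are analysed, the low ends with equal sizes fall to 5.2%, 7.5% and 17.3%.

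**Simulation of the two named analyses.** No true difference; 663 versus 950 patients; target attainment about 0.65; hospital-size coefficient of variation 0.5; two imbalanced patient covariates in the propensity score; 3000 runs per setting and two seeds. Mantel-Haenszel stands in for the stratified method, which the protocol does not name. Rejection rates at nominal 5%:

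| Analysis, model-based SE | CTRL hospitals | ICC 0.001 | ICC 0.01 | ICC 0.05 |
|---|---|---|---|---|
| Logistic with propensity covariate | 15 | 4.9% | 10.6-10.9% | 28.4-29.6% |
| Logistic with propensity covariate | 8 | 5.2-5.6% | 13.6% | 36.9-37.0% |
| Propensity deciles | 15 | 4.8-5.2% | 10.3-10.5% | 28.2-29.8% |
| Propensity deciles | 8 | 5.1-5.7% | 13.3-13.5% | 36.8-37.0% |

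Both analyses had the propensity score available, and the inflation remained.

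**Does clustering by hospital repair it?** Same simulation, t reference on K − 2 degrees of freedom (K = all hospitals), at ICC 0.001 / 0.01 / 0.05:
- Cluster-robust variance with only a K/(K − 1) factor: 5.2 / 5.9 / 6.5% with 15 CTRL hospitals and 6.6 / 6.9 / 7.8% with 8.
- With the Mancl-DeRouen correction: 4.0 / 4.0 / 4.3% and 3.8 / 4.4 / 4.5%.

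Clustering removes most of the inflation. With few hospitals the simple factor stays somewhat liberal, so a small-sample correction is worth having.

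**The case against.** The strongest reply is that the variance estimator is an ordinary SAP item and that Section 10 defers the formal methods to the SAP. The protocol nowhere prescribes independent-patient standard errors. A clustered variance is compatible with both named analyses, and no sentence would have to be reversed to adopt it. This stands in part: the defect depends on what the SAP adds. It does not dispose of the point. Section 10 does more than defer: it names two outcome models for the comparison the study exists to make and describes them at patient level. A SAP that formalised those lines as written would carry the problem over.

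The second reply is that the size rests wholly on assumptions. This stands. An ICC of 0.05 at 65% attainment means a between-hospital standard deviation of sqrt(0.05 × 0.65 × 0.35) = 0.107. The range 0.65 ± 1.96 × 0.107 is about 44% to 86%, a wide spread to remain after adjustment. PENELOPE hospitals also followed one stepwise protocol, which could make them more alike and so strain the assumption of a common ICC. At ICC 0.001 there is practically no inflation. None of this shows that the ICC is zero: common research procedures and a similar hospital type (Section 6a) do not make target attainment equal.

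A reader might infer more: that the final analysis will be wrong, that its error rate is 20-36%, or that ignoring hospital biases the odds ratio. The documents support none of these. The SAP may already cluster by hospital, the ICC is not given, and the point concerns the standard error, not the point estimate.

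**Conclusion.** The point holds in conditional form. That each hospital belongs to one cohort only is documented, and no section of the protocol allows for hospital. Run as described, adjusted or unadjusted, the comparison understates the standard error whenever residual between-hospital variation exists. The two adjusted analyses matter only if both of Section 10's conditions are met; otherwise the unadjusted comparison carries the same weakness.

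The error figures rest on the assumed ICC, the assumed number of CTRL hospitals and the other assumptions listed with the calculation. Since the true SE exceeds the model SE by 10% at an ICC of only 0.003 (8 CTRL hospitals, 1200 patients) to 0.008 (30 hospitals, 700 patients), the plan should be corrected even though the effect may prove negligible.

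**What to change.** State in Section 10 that every between-cohort outcome comparison, adjusted or not, uses standard errors clustered by hospital with a small-sample correction.

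- **Logistic model:** a cluster-robust variance, or GEE with independence working correlation, with a t reference based on the number of hospitals. The odds ratio itself does not change.
- **Decile analysis:** an equivalent hospital-level method.
- **Missing values:** if multiple imputation is used, apply the clustered variance within each imputed dataset before pooling.
- **Propensity model:** keep hospital out of it, because hospital determines cohort exactly. Hospital fixed effects in the outcome model fail for the same reason.
- **Reporting:** give the number of hospitals per cohort.

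The exact correction can be left to the SAP. If the SAP already covers this, a cross-reference in Section 10 is enough.

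The cost is a short addition to Section 10, the matching specification in the SAP, and wider intervals. A hospital identifier is needed in both datasets. For CTRL it can be inferred from the centre-level data entry in Section 13e; for PENELOPE it has to be confirmed. The change corrects precision only. It does not remove confounding by systematic differences between the two sets of hospitals, and the report should say so.
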